Clinical interview. Trained clinical interviewers will conduct the CAPS-5 interview to establish PTSD diagnosis and SCID-5 interview to establish insomnia diagnosis. This will take place over phone or video. The SCID-5 will also be used to rule out diagnostic exclusion criteria and establish comorbid mental health conditions for data analytic purposes. A brief medication interview will be conducted to obtain information about recent and current medication use. Interviews will be audio-recorded and reviewed by the Stress and Health Research Program's clinical assessment supervisor \*This is solely for research purposes.

Baseline prospective sleep data. Once eligibility is established, the Veteran will be shown how to complete a sleep diary. He or she will then record one week of baseline sleep data. Research staff will email the Veteran a link to enter sleep diary data via Qualtrics. The Veteran's PAP setup appointment (if needed) and treatment schedule will be planned. \*This is for research purposes; however, please note that completing a sleep diary is also part of routine care.

**Actigraphy.** The actigraph is a device worn on the risk to measure time asleep vs. awake. A subset of participants will be asked to wear the actigraph. The information will be used solely for research purposes. It is not part of the treatment.

**Baseline appointment**. The Veteran will complete pre-treatment measures. He or she will be randomized to either AIR or SE. \* Many of the pre-treatment measures are completed as part of routine care, but some are added for research purposes.

**Randomization procedure.** A block-randomization procedure will be used to assign participants to AIR or SE in a 1:1 ratio. Block sizes will be a random permutation of 4 and 6. Statistical consultant [REDACTED] will produce the computer-generated list. Each therapist will have his or her own randomization list. The randomization to treatment is for research purposes.

**Weekly assessment.** At the start of each treatment appointment, the Veteran will complete two self-report questionnaires assessing sleep (ISI and ESS). The Veteran's PAP adherence data and actigraphy data will also be downloaded or requested verbally. A copy of the Veteran's sleep diary will be obtained. At his or her final treatment appointment, the Veteran will be asked to complete a sleep diary to submit at the Post-Treatment

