Assessment appointment. In addition, at weeks 1, 3 and 5, the Veteran will complete the primary and secondary functioning outcome measures (WHOQOL-BREF and FOSQ-10.) \*Completion of ISI and ESS, sleep diary data, and PAP adherence are part of routine care and will also be used for research purposes. The additional WHOQOL-BREF AND FOSQ-10 at weeks 1, 3 and 5 are for research purposes.

**Post-Treatment Assessment.** One week following his or her final treatment appointment, the Veteran will attend the post-treatment assessment appointment via phone or video. He or she will turn in the sleep diary with data from the preceding week. He or she will turn in the actigraphy device. The Veteran will complete post-treatment questionnaires. A trained, blinded clinical interviewer will repeat the CAPS-5 interview (current symptoms only) and SCID-5 (insomnia portion only) and inquire about medication changes. The Veteran will complete a brief feedback interview about their treatment experience with study staff. The Veteran's PAP adherence data will be downloaded or provided verbally. \*This is for research purposes.

**3-Month Follow-Up Assessment.** Veterans will complete the 3-month follow-up questionnaires. PAP adherence data will be downloaded or provided verbally. If the Veteran's PAP device does not have a functional modem, the study team will arrange for the Veteran to provide their SD card for data download. The data will be uploaded to the appropriate clinical data monitoring system and the SD card will be returned to the Veteran. Veterans' charts will be checked to track PAP follow-up appointment attendance, if applicable. Veterans will be sent a sleep diary to complete the week prior to this appointment and will submit it at this appointment. \*This is for research purposes. However, review of PAP adherence data at 3-month follow-up is also part of routine care in the Sleep Clinic.

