#### **Intervention Descriptions**

Apnea and Insomnia Relief (AIR). This treatment will be offered over six sessions. All six appointments will be conducted via telehealth and will last 60 minutes. The main components of the AIR protocol are (a) psychoeducation, (b) motivational interviewing, (c) PAP adherence strategies, and (d) cognitive behavioral therapy for insomnia. All of these components are based in established strategies from other behavioral interventions but have not been evaluated in a combined protocol. The table beneath this description provides for a session-by-session overview of the treatment.

**Psychoeducation.** Education about insomnia, sleep apnea, and PTSD is primarily provided in the first session, though it is interwoven into subsequent sessions based on each Veteran's needs. Sleep apnea education involves review of what sleep apnea is, how the severity of sleep apnea is measured (AHI), and understanding what his or her own AHI means (e.g., "I stop breathing 25 times each hour.") Veterans identify how sleep apnea affects functioning and quality of life, including nighttime symptoms, daytime symptoms, and impact of physical health. Veterans then learn about how PAP helps sleep apnea. Insomnia education involves definition of insomnia; in particular, early, middle, and late insomnia are defined, and the Veteran identifies which type(s) of insomnia he or she is experiencing. An emphasis is placed on how sleep apnea affects quality of sleep, while

insomnia may impact quantity of sleep. A brief review of PTSD symptoms, particularly sleep-related symptoms, is integrated into this component.

**Motivational interviewing.** Strategies to increase motivation for treatment will be employed throughout treatment as needed, but motivational interviewing is a particularly strong focus in the first session. The therapist will help the Veteran identify benefits to engaging treatment, both in the short-term and long-term. Veterans will be guided through specifying goals for treatment. They will also identify potential barriers to treatment as well as solutions to these barriers.

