### Apnea and Insomnia Relief (AIR) session content

Session	Content
1	Psychoeducation about sleep apnea, insomnia, and PTSD; assessing/increasing motivation and identifying goals for treatment; learning to complete sleep diary
2	Continued motivational interviewing; Reviewing PAP experience; introducing PAP desensitization (in-session and at home) if needed; reviewing sleep diary; learning about sleep restriction
3	Reviewing PAP experience; continuing PAP desensitization; reviewing sleep diary; introducing stimulus control; continued motivational interviewing, if needed
4	Reviewing PAP experience; continuing PAP desensitization; reviewing sleep diary; sleep hygiene; continued motivational interviewing, if needed
5	Reviewing PAP experience; continuing PAP desensitization; reviewing sleep diary; cognitions about sleep; relaxation strategies; continued motivational interviewing, if needed
6	Reviewing PAP experience, continuing PAP desensitization; reviewing sleep diary; reviewing progress and relapse prevention

**Sleep Education Control (SE).** The control treatment will also be offered over 6 sessions via telehealth, to match time with the attention provided in the AIR condition. The protocol is an adaptation of the non-directive sleep education control condition in a study of CBT for insomnia among older adults at the Greater Los Angeles Healthcare System. Topics covered include the sleep cycle, sleep across the lifespan, sleep and the mind, evening activities and the sleep environment, and daytime activities and sleep. The table beneath this description provides for a session-by-session overview of the treatment.

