outliers will be conducted to evaluate influence on outcomes. Primary analyses will be unadjusted intent-to-treat analyses, with all subjects randomized to a treatment condition included. We will use linear mixed models, which are robust to data missing at random, to accommodate missing data due to dropout. Demographic and other baseline variables that show large group imbalances despite randomization will likewise be entered as covariates in a secondary sensitivity analysis, but will not be included in the primary analyses. Substantial differences in inferences supported by the primary and secondary analyses would indicate a potential problem of randomization failure, and would warrant caution in interpreting results of the primary analyses

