Analyses for PAP adherence: PAP adherence will be measured via device data capture. The primary metric used to measure this will be average hours of PAP use in the past 7 days. This will be measured starting at session 1 and will continue through post-treatment, and again for 1 week at follow-up. A linear mixed model as described above for the ISI will be estimated for PAP adherence. The hypothesis will be tested by the significance of the group difference in marginal means at post-treatment derived from the full model. The difference in marginal means at post-treatment will be divided by the pre-treatment standard deviation to calculate the standardized effect size. Durability of effects at 3 months will be tested by comparing model-adjusted marginal effects for the two groups at follow-up. Effect size of treatment at 3 months will be calculated from the marginal effect of group at follow-up divided by the standard deviation of week 1 adherence scores. Hypothesis 2a: Veterans receiving the behavioral sleep treatment will report at least moderate agreement with items on the Feasibility and Acceptability Questionnaire. Analyses: Descriptive statistics will be calculated for each item of the Feasibility and Acceptability questionnaire, provided in the Appendix. The mean response to each item will be the primary metric for evaluation of this hypothesis. A mean in the range of 4.0 to

**Hypothesis 2b:** There will be lower dropout in the AIR condition compared with the SE condition.

**Analyses:** We will conduct a chi-square analysis to compare dropout in the two conditions (completed all six sessions vs. not).

**Hypothesis 2c:** There will be greater engagement in apnea care in the AIR condition compared with the SE condition.

**Analyses:** We will conduct a chi-square analysis to compare how many Veterans attend their first PAP follow-up appointment with a sleep technician or sleep NP in the two conditions.

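### The primary post-treatment visit is dated from each Veteran's own final appointment, with no rule for Veterans who stop before session 6

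*Combined protocol and SAP*

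**What the plan says.** Under Data Collection Procedures, the Post-Treatment Assessment paragraph places the visit, held by phone or video, at "One week following his or her final treatment appointment". The Weekly assessment paragraph uses the same anchor for the diary: "At his or her final treatment appointment, the Veteran will be asked to complete a sleep diary to submit at the Post-Treatment" visit. Neither gives a study week, a visit window or a rule for a Veteran who stops before the last planned session. The 3-Month Follow-Up paragraph does not say from what date the three months run.

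Both arms have six planned sessions. For AIR, "This treatment will be offered over six sessions"; for sleep education (SE), "The control treatment will also be offered over 6 sessions via telehealth". During treatment, "at weeks 1, 3 and 5, the Veteran will complete the primary and secondary functioning outcome measures"; this appears among the assessments made at treatment appointments.

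Under Hypothesis Testing (1a), the primary model takes the pre-treatment score as a covariate. Its outcome time points are week 3, week 5, post-treatment and follow-up, entered as categories. The test is the baseline-adjusted arm difference at post-treatment.

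The Statistical Analysis Plan paragraph calls the primary analyses intent-to-treat, "with all subjects randomized to a treatment condition included", and relies on linear mixed models under missing at random (MAR) for data lost to dropout. Dropout is defined under Hypothesis 2b as not completing all six sessions. The hypothesis itself reads: "There will be lower dropout in the AIR condition compared with the SE condition". The Dropout paragraph also plans for higher dropout in AIR, and reports that in the sponsor's earlier trials dropout came mostly straight after randomization.

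**The concern.** The date of the primary endpoint depends on how long a Veteran stays in treatment, which is decided after randomization and may be affected by arm. For completers this does no harm. For early stoppers the plan does not say when the visit falls, or whether there is one.

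Two things are at stake. The first is selective loss: if stopping sessions also means leaving assessment, the primary comparison rests on those who stayed. The second is comparability in time: if stoppers are assessed soon after their last attended session, scores taken at different times since randomization share one category. Loss is the more important of the two, because the MAR model can use only the outcome rows that a Veteran has.

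**Working it through.** The documents give no dropout rate, SD, alpha or target effect, so there is no figure of the plan's own to reproduce. Weekly sessions in weeks 1 to 6 are an assumption; the Weekly assessment heading implies them but no spacing is stated.

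**Step 1. Date of the visit and rows in the model.** With last attended session k, the last-attended reading puts post-treatment at week k + 1. A completer is seen at week 7, so the visit is 7 − (k + 1) = 6 − k weeks early. The last column assumes that the week 3 and week 5 scores are taken only at appointments.

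| Last session attended | Post-treatment week (last-attended reading) | Weeks early | Outcome rows before post-treatment |
|---|---|---|---|
| 0 | no date | – | none |
| 1 | 2 | 5 | none |
| 2 | 3 | 4 | none |
| 3 | 4 | 3 | week 3 |
| 4 | 5 | 2 | week 3 |
| 5 | 6 | 1 | week 3, week 5 |
| 6 | 7 | 0 | week 3, week 5 |

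Under the session-6 reading, every row except the last has no dated post-treatment visit.

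**Step 2. What the primary model can use.** The baseline score is a covariate, not an outcome, and the week 1 score is not among the outcome time points. A Veteran who stops after 0, 1 or 2 sessions and has no later assessment therefore supplies no outcome row and drops out of the fit. A Veteran who stops after 3, 4 or 5 sessions supplies one or two rows, and MAR modelling can use those. The early pattern that the sponsor reports from previous trials belongs to the first group.

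**Step 3. Size of the loss (assumed rates).** Take dropout of 10% in AIR and 30% in SE, with 40 per arm: 4 and 12 stoppers, leaving 36 and 28 if all are lost. The difference detectable with 80% power at two-sided 0.05 (unadjusted two-sample approximation, in SD) is (1.96 + 0.84) × √(1/n₁ + 1/n₂):

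- 40 and 40: 2.80 × 0.2236 = 0.63 SD
- 36 and 28: 2.80 × 0.2520 = 0.71 SD

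This is lost precision only. Bias from selective loss cannot be computed from the documents.

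**Step 4. Size of the timing bias (last-attended reading only).** Assume no true effect, a common linear improvement of s SD over the 6 weeks from week 1 to week 7, and stoppers seen on average e weeks early. Then bias = (d_SE − d_AIR) × s × e / 6, where d is the dropout share.

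- 10% AIR, 30% SE: from 0.20 × 0.3 × 1/6 = 0.01 to 0.20 × 0.8 × 5/6 = 0.13 SD in favour of AIR; 0.05 SD at s = 0.5, e = 3
- 10% AIR, 20% SE: 0.005 to 0.07 SD in favour of AIR
- equal dropout: 0
- 30% AIR, 10% SE: 0.01 to 0.13 SD against AIR

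**Step 5. Would Hypothesis 2b reveal an imbalance?** With 40 per arm at two-sided 0.05, power is about 61% for 10% against 30%, and 24% for 10% against 20%. A non-significant result would not show that dropout was balanced.

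**The case against.** The strongest reply is that *final* naturally means session 6. Staff hand out the diary at that appointment, which they can do only if they know it is the last; the treatment schedule is planned in advance; and session 6 is the closing review in both arms. This is persuasive, and it means that early measurement is only one possible reading. It does not remove the gap, because on that reading stoppers have no date at all. A planned-date reading would put them on time, but the protocol never says so.

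A second reply is that the plan foresees missing data from dropout and names a method. That stands for Veterans with a week 3 or week 5 score, but not for those with no outcome row (Step 2).

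A reader might go further than the documents allow in four ways:

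- *The visit timing favours AIR.* Hypothesis 2b is a prediction without rates, and the Dropout paragraph allows for the reverse.
- *Stoppers' visits duplicate the week 3 or week 5 rows.* Those scores are described among assessments at treatment appointments, so a Veteran who stopped after session 2 would probably have no week 3 row to duplicate.
- *The plan contradicts its intent-to-treat statement.* The same paragraph expects missing data, so this is a shortfall in delivering the stated population, not a contradiction.
- *The primary test is undermined by timing.* Step 4 reaches 0.13 SD only with a 20-point dropout gap, steep improvement and every stopper leaving after session 1.

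Finally, moving completers to a date counted from randomization would give up their constant interval after treatment ends. That is a real trade-off, and the point does not require it.

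**Conclusion.** The point holds as a gap in the assessment rule for early stoppers. The primary time point has no study week, no window and no provision for Veterans who stop before session 6; those who attend no session have no date under the literal wording. As the primary model is specified, stoppers without any assessment from week 3 on contribute nothing, so the analysis would not cover all randomized Veterans.

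The direction of any bias is unknown. The timing component is probably small and arises only on the last-attended reading. Selective loss matters more, but it can be sized only through assumed dropout: at 10% against 30%, up to 16 of 80 Veterans would be lost. These conclusions rest on weekly sessions, on on-treatment scores being collected only at appointments, and on the assumed rates shown.

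**What to change.** Keep the present rule for Veterans who complete session 6. Add to the Post-Treatment Assessment paragraph that every randomized Veteran who stops early, including one who attended no session, is still invited to the assessment one week after the planned date of session 6, within a stated window. Date the 3-month follow-up for these Veterans from that same point. State in the Statistical Analysis Plan that their scores are analysed under those nominal visits.

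The planned date should be available for everyone, since the treatment schedule is drawn up once eligibility is established. Post-treatment visits are already held by phone or video. The cost is protocol wording and some extra contact effort by existing staff. Some stoppers will decline, so the change reduces selective loss but does not remove it.

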Objective: Aim 1: Conduct a pilot RCT comparing AIR (n = 40) with sleep education (control condition; n = 40) for Veterans with OSA, insomnia, and PTSD. Hypothesis 1a: Veterans receiving AIR will demonstrate improved quality of life (WHOQOL-BREF; primary outcome) and functioning (FOSQ-10; secondary outcome) compared with control at post-treatment and follow-up assessments. **Hypothesis 1b**: Veterans receiving AIR will demonstrate greater reduction in symptoms of insomnia (ISI and actigraphy) and PTSD (CAPS-5), and greater adherence to PAP (device data capture) compared with control at post-treatment and follow-up.

Aim 2: Evaluate the feasibility and acceptability of AIR. Participants will complete a Feasibility and Acceptability Questionnaire (FAQ) and follow-up interview based on their questionnaire responses. Topics will include content of treatment as well as experience completing the treatment delivered via telehealth. Examination of treatment dropout and attendance at other PAP-related appointments will also be monitored to determine whether the treatment facilitated increased engagement in care. Hypothesis 2a: Veterans receiving AIR will report at least moderate agreement with items on the FAQ. Hypothesis 2b: There will be lower dropout in the AIR condition compared with control. Hypothesis 2c: There will be greater engagement in apnea care in the AIR condition compared with control

**Aim 3 (Exploratory): Evaluate moderators of treatment outcome.** I will evaluate the data for trends indicating potential moderators of treatment outcomes, such as sleep apnea severity or concurrent medication use.

Design: First, I will conduct a randomized controlled trial of AIR and a sleep education control condition. The primary outcome will be quality of life. Next, I will solicit Veteran feedback to assess the feasibility and acceptability of AIR and evaluate measures of engagement in care. Finally, I will identify moderators of treatment outcome, which may help target Veterans for whom the treatment needs further refinement.

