PAP adherence strategies. The Veteran will typically receive their PAP on the same day as their first treatment session. When the Veteran receives his or her PAP device, a certified sleep technician and/or respiratory therapist trained in sleep instructs the Veteran in the device's use and care. At the first AIR appointment, the therapist reviews with the Veteran how he or she can check his or her progress on the device itself. The therapist and Veteran work together to identify problems with and barriers to PAP use each week. This may include physical problems that require a return visit to the sleep technician (e.g., mask air leak from poor fit), and the therapist will prompt the Veteran to arrange an appointment. Another barrier that may be addressed is difficulty remembering to put the mask on before bed; the therapist will assist the Veteran in setting up reminders to facilitate PAP use. Should the Veteran experience anxiety, claustrophobia, or general discomfort (not stemming from a physical issue requiring further assessment by the sleep technician) related to PAP, which is not uncommon with PTSD or anxiety, the therapist will guide the Veteran though PAP desensitization. PAP desensitization will also be advised if the Veteran is removing the mask in the middle of the night.

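### PAP adherence is defined as device data capture, yet session, post-treatment and 3-month values may be given verbally, with no source rule and an SD-card fallback stated only at 3 months

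*Combined protocol and SAP*

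**What the plan says.** All references are to the combined protocol and SAP.

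- **Definition.** Hypothesis 1b, under Objective, predicts "greater adherence to PAP (device data capture) compared with control at post-treatment and follow-up". Analyses for PAP adherence repeats the source, "PAP adherence will be measured via device data capture", and gives the metric: "The primary metric used to measure this will be average hours of PAP use in the past 7 days". The hypothesis is tested on the group difference at post-treatment, and durability is examined at 3 months.
- **Treatment sessions.** Weekly assessment says: "The Veteran's PAP adherence data and actigraphy data will also be downloaded or requested verbally".
- **Post-treatment.** Post-Treatment Assessment says: "The Veteran's PAP adherence data will be downloaded or provided verbally". No fallback is given for a device that cannot transmit.
- **3 months.** 3-Month Follow-Up Assessment again allows either route and then adds a step for some devices: "PAP adherence data will be downloaded or provided verbally. If the Veteran's PAP device does not have a functional modem", then "the study team will arrange for the Veteran to provide their SD card for data download".
- **What differs by arm.** PAP adherence strategies states that at the first AIR appointment "the therapist reviews with the Veteran how he or she can check his or her progress on the device itself". AIR also includes motivational interviewing, weekly work on barriers to PAP use, and a review of PAP experience in sessions 2 to 6. The Sleep Education (SE) session table lists no PAP or device content.
- **Other uses of the values.** Exploratory Analyses sorts Veterans into three adherence bands (under 1 h, 1 to 4 h, over 4 h) and repeats the insomnia analyses in those not adherent to PAP.

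**The concern.** Device capture matters for an adherence outcome because the measured hours do not depend on what the participant remembers or wishes to report. The procedures allow a route that may lack that protection, including at the visit where the hypothesis is tested. They do not say what a verbal value is, how it is checked, or how the analysis treats it, so recalled hours could enter the model labelled as device data.

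This would be mainly noise if reporting error were alike in the two arms. There is reason to think it may not be. Blinding is stated only for the clinical interviewer, and Veterans know the content of the sessions they attend. AIR reviews usage on the device and coaches adherence. An AIR Veteran might report more accurately because of the first, or more favourably because of the second. A measurement difference could then look like a difference in use, or hide one. Misreported hours could also move Veterans across the exploratory cut-points and change who is in the non-adherent subset.

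**Working it through.** The plan gives no SD, effect size or power for adherence, so there is no stated figure to reproduce. The finding rests on comparing the text; the arithmetic only shows scale.

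**Text comparison**

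| Time | Source named for the analysis | Collection allowed | SD-card route stated |
|---|---|---|---|
| Sessions | Device | Download or verbal | No |
| Post-treatment (main test) | Device | Download or verbal | No |
| 3 months (durability) | Device | Download or verbal | Yes, if the modem does not work |

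The plan foresees devices that cannot be downloaded remotely, but provides for them only at the last visit. No section requires a display reading, a source field, or separate handling of verbal values.

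**Illustration of scale**

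From the documents: 40 Veterans per arm. Assumed: SD of hours 2 to 3 h, two-sided alpha 0.05, verbal share f of 10%, 25% or 50% (equal in both arms), and an arm difference d in mean reporting error of 0.5 to 1.0 h.

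1. Standard error = SD × √(2/40). For SD 2 h this is 0.447 h; for SD 3 h it is 0.671 h.
2. Difference detectable with 80% power = (1.960 + 0.842) × standard error = 1.25 h (SD 2) to 1.88 h (SD 3).
3. Bias = f × d.
4. Chance of a significant result with no true difference = Φ(bias/SE − 1.96) + Φ(−bias/SE − 1.96).

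| Verbal share | Bias (h per night) | False-positive rate over SD 2 to 3 h |
|---|---|---|
| 10% | 0.05 to 0.10 | 5.1% to 5.6% |
| 25% | 0.13 to 0.25 | 5.4% to 8.6% |
| 50% | 0.25 to 0.50 | 6.6% to 20.1% |

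Worked example: f = 25%, d = 1.0 h and SD = 2 h give a bias of 0.25 h. Then 0.25/0.447 = 0.559, and Φ(−1.401) + Φ(−2.519) ≈ 0.086. If the same bias ran against a true difference of 1.25 h, power would fall from 80% to Φ(2.802 − 0.559 − 1.960) = Φ(0.283) ≈ 61%.

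This is a simple two-sample approximation. It ignores dropout and any precision that the mixed model gains from repeated measures.

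**The case against.** **A verbal value may still be device data.** A reader might infer that the plan mixes objective with self-reported hours. The documents do not establish that. What is requested is adherence data; the same sentence covers actigraphy, which a Veteran could hardly recall; and usage can be checked on the device. A verbal value could be a display reading relayed by phone or video. This objection stands in part: recall is not shown, but neither is it excluded.

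**SE Veterans are not shown to be unable to read their device.** A sleep technician or respiratory therapist teaches operation and upkeep when the device is handed over, and nothing limits this to AIR. SE Veterans are also asked for the data at their appointments, and a table of teaching topics says little about data collection. This stands. What the text supports is narrower: only the AIR content includes this review and coaching, so a difference in error is possible.

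**The 3-month visit is neither clean nor irrelevant.** A reader might take verbal values to be confined to treatment and post-treatment. They are allowed at 3 months too, although the SD-card step reduces the problem there. That step might also recover the post-treatment week, if the card holds it. The documents do not say whether it does.

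**Discarding every verbal value would be excessive.** It would throw away accurate display readings in an 80-person pilot and tie missingness to modem status. This stands, and the fix below does not ask for it.

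**Conclusion.** The conflict between definition and procedure is real and should be resolved. Adherence is specified as device data but may be supplied verbally at every assessment, with no reading rule and no record of source, and the SD-card route is not stated for the visit of the main test.

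The size is unknown. It depends on the verbal share and on the arm difference in reporting error, and the documents give neither. Under the assumptions above the effect is negligible at a 10% share and becomes material only towards a 50% share with a full hour's difference in error. The direction is also unknown, so a reader should not conclude that the design favours AIR; a true difference could equally be masked.

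The reach is limited. Adherence is one of the Hypothesis 1b outcomes, along with the exploratory analyses that reuse it. The WHOQOL-BREF psychological domain analysis under Hypothesis 1a is not built on these values.

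**What to change.** 1. In both arms, obtain the treatment and post-treatment nights by modem or SD card. For devices with no working modem, either arrange a card return at post-treatment or extract those nights from the card already collected at 3 months, once it is confirmed that the card keeps them.
2. In the Hypothesis 1b adherence analysis, use the downloaded value in place of any verbal one for the same period. Carry the same rule into the exploratory adherence bands and the non-adherent subset.
3. Where no download can be obtained, accept a verbal value only if it is read from the device display. Specify the quantity to be read so that it matches the 7-day metric. Recalled hours are treated as missing.
4. Record the source of every value (modem, card or display), and report the share of each by arm and visit.
5. Report a sensitivity analysis restricted to downloaded values.
6. Amend the session, post-treatment and 3-month procedures and the adherence analysis so that they describe the same measure.

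**Cost.** The change needs one possible extra card return for Veterans without a working modem, one source field and some SAP wording. Some weekly values may be missing if card history is incomplete. The planned linear mixed model can accommodate these under its missing-at-random assumption.
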